2. STUDY DESIGN

Figure 1 Study design overview

S = Screening Visit; V = Visit; PC = Phone contact; D = Day; FU = Follow-up; BS (1) = blood sample for humoral immunogenicity; BS (2) = blood sample for cell-mediated immunogenicity (CMI), this blood sample will only be collected from a sub-cohort of subjects; BS (3) blood sample for biomarkers; SP = sputum sample

The allowed maximum interval between Screening Visit and Visit 1 is 29 days. If a delay occurs for an eligible subject so that the interval exceeds 29 days, some study procedures performed during the Screening Visit needs to be repeated within 7 days (see Table 6 of the protocol for more details).

* An AECOPD visit should be scheduled as soon as possible after the onset of AECOPD symptoms (max 96 hours after and, if applicable, preferably before starting treatment with antibiotics) During this visit blood and sputum samples will be collected. In addition, follow-up phone call(s) and/or visit(s) will take place to determine the end of the AECOPD. These contacts will take place at least every 2 weeks until the AECOPD is resolved.

Investigational vaccine and placebo will be administered in addition to standard of care.

- **Experimental design:** Phase IIB, randomised, observer-blind, placebo-controlled, multi-centric study with two parallel groups.
- **Duration of the study:** for each subject enrolled, the study will last approximately 15 months from Visit 1 up to study completion (Visit 8).
 - Epoch 001: Screening Visit (Day -28 to Day -1).
 - Epoch 002 : Primary starting at Visit 1 (Day 1) and ending at Visit 8 (Day 451).
- **Primary completion Date (PCD):** Last Subject Last Visit (LSLV) from Visit 8 (Day 451) or last visit/contact of Epoch 002.
- **Study groups:**
 - **10-10-3-AS:** Approximately 300 subjects receiving two doses of the AS01_E-adjuvanted GSK Biologicals' NTHi-Mcat investigational vaccine containing 10 µg of PD, 10 µg of PE-PilA, and 3.3 µg of UspA2.
 - **CONTROL:** Approximately 300 subjects receiving two doses of placebo (PBS).

CONFIDENTIAL

207489 (NTHI MCAT-002)

Statistical Analysis Plan Amendment 2 FDA Final Draft

The following group names will be used for the statistical analysis

Table 1 Study groups and epochs foreseen in the study

Group order in tables	Number of subjects	Group label in tables	Group definition for footnote
1	~300	10-10-3-AS	2 doses of AS01E-adjuvanted NTHI/Mcat vaccine containing 10 mcg of PD, PE-PiA and 3 mcg of UspA2

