2	~300	PLACEBO	2 doses of phosphate buffered solution

- **Sampling schedule:**

- **Blood samples for assessment of humoral immunogenicity** will be collected from all subjects at Visit 1 (Day 1), Visit 2 (Day 31), Visit 3 (Day 61), Visit 4 (Day 91), Visit 6 (Day 271), Visit 8 (Day 451) and at each AECOPD visit from first vaccination to study conclusion.
- **Blood samples for assessment of cell-mediated immunogenicity (CMI)** will be collected from all subjects in the CMI sub-cohort (approximately 60 subjects in each group) at Visit 1 (Day 1), Visit 4 (Day 91), Visit 6 (Day 271) and at Visit 8 (Day 451).
- **Blood samples for biomarkers** will be collected from all subjects at Visit 1 (Day 1), Visit 8 (Day 451) and at each AECOPD visit from first vaccination to study conclusion.
- **Blood sample for haematology profile** will only be collected at Visit 1.
- **Sputum samples for PCR (all subjects) and culture** (50% of subjects) will be collected from all subjects at Visit 1 (Day 1), Visit 4 (Day 91), Visit 5 (Day 181), Visit 6 (Day 271), Visit 7 (Day 361), Visit 8 (Day 451) and at each AECOPD visit from first vaccination to study conclusion.

Other assessments:

- **COPD symptoms:** All subjects will be asked to record COPD symptoms in their electronic Diary Card:
 - Daily in the morning throughout the study (including during AECOPD): **morning symptoms questionnaire**.
 - Daily in the evening throughout the study (including during AECOPD): **EXACT-PRO questionnaire**.
- **HRQOL assessments:**
 - All subjects will be asked to complete the COPD assessment test (CAT) at the Screening Visit (pre-Day 1), Visit 6 (Day 271), Visit 8 (Day 451) and at each AECOPD visit from first vaccination to study conclusion.
 - All subjects will be asked to complete St. George's Respiratory Questionnaire for COPD patients (SGRQ-C) at the Screening Visit (pre-Day 1), Visit 6 (Day 271), at Visit 8 (Day 451) and at each AECOPD visit from first vaccination to study conclusion.

CONFIDENTIAL

207489 (NTHI MCAT-002)

Statistical Analysis Plan Amendment 2 FDA Final Draft

Pre- and post-bronchodilator spirometry assessments will be done for all subjects at the Screening Visit (pre-Day 1), Visit 6 (Day 271) and at Visit 8 (Day 451).

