6.6.2. Health related quality of life (QOL)

The following analysis are exploratory and a p-value <0.1 will be considered statistically significant, however 2-sided 95% CIs will be computed to show precision of estimation. All comparisons should be interpreted with caution considering that there will be no adjustment for multiplicity.

For each of the following questionnaire missing items will not be imputed and subjects with partial data will be excluded.

EXACT-PRO daily score

The EXAcerbations of Chronic pulmonary disease Tool (EXACT) constitutes of 14 items which are patient-reported outcome (PRO) via daily diary.

All EXACT-pro scores will be divided in to the following periods:

- Screening: scores collected between screening and Visit 1 (Baseline)
- Treatment: scores collected between Visit 1 and Visit 4 (i.e., 1 month post-Dose 2)
- Exacerbation: scores collected during the start date of an exacerbation until resolution.
- Follow –up: scores collected between Visit 4 (1 month post-Dose 2) until study completion (one year after - Visit 8).
- Follow-up will be also divided by 3 months sub period:
 - from Visit 4 to Visit 5 (Day 91 to Day 180)
 - from Visit 5 to Visit 6 (Day 181 to Day 270)

CONFIDENTIAL

207489 (NTHI MCAT-002)

Statistical Analysis Plan Amendment 2 FDA Final Draft

- from Visit 6 to Visit 7 (Day 271 to Day 360)
- from Visit 7 to Visit 8 (Day 361 to Day 450)

Descriptive statistics

For each subject the average score across all days, within each period is computed. The mean score will be reported as descriptive statistics within each group (i.e., vaccine and placebo). N, mean, SD, median, min and max, on the **EXACT-PRO** average scores will be tabulated during all (stable) periods and during exacerbations.

Between groups comparison

At each period and sub period the two groups will be compared using an ANCOVA model, with the baseline value (i.e., score at screening) as covariate and treatment as fixed factor.

Note: EXACT-PRO baseline score at screening will be computed as the average within-patient score collected between screening Visit and Visit 1. If fewer than 4 days scores are available, the EXACT-PRO baseline score cannot be calculated, and it will result as missing.

COPD Assessment Test (CAT)

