11.3. Randomization method and minimization algorithm

Subjects are randomised using a centralised randomisation system on internet (SBIR) at first dose. The system incorporates a minimization algorithm based on White SJ and Freedam LS method [[White SJ](#), Freedman LS, 1978] and it is described below:

Notation:

- k input values to be used for minimization, each with a weight w_k ($k=1, \dots, K$) and l_k variants.
- i treatment groups applicable to stratum the subject has been identified with randomization ratio a_1, \dots, a_i
- D: percentage of determinism
- W: weight assigned to each minimization factor

In this study k=4: Country, GOLD grade, History of exacerbation and Age group defined as :

COUNTRY [8 variants]: BE CA FR DE IT ES UK US

GOLD [3 variants]: 2 3 4

AGECAT [2 variants]: 40-60 61-80

HIST_ES [2 variants]: < 2 >=2

i=2: VACCINE and PLACEBO with randomization ratio 1:1 ($a_i=1$)

D=90%

W=1 for each variable

CONFIDENTIAL207489 (NTHI MCAT-002)
Statistical Analysis Plan Amendment 2 FDA Final Draft

Algorithm:

For a new subject in criteria levels $s_1 \dots s_k$ **Step 1: Minimization computation**

Step 1.1: Initialize Problem flag to 0

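### The EXACT-PRO ANCOVA leaves out the four minimisation factors, so its intervals may be wider and its test more conservative than they need be; handling of a missing baseline is also not stated

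*SAP*

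**What the plan says.** **Model.** In SAP Amendment 2, section 6.6.2, the two groups are compared at each period and sub-period "using an ANCOVA model, with the baseline value (i.e., score at screening) as covariate and treatment as fixed factor". No other term is named.

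**Allocation.** Section 11.3 describes the minimisation: "In this study k=4: Country, GOLD grade, History of exacerbation and Age group", each with weight 1, with 90% determinism and a 1:1 ratio.

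**Other models.** The primary negative binomial model (6.3.1.1.1) and the bacteriological model (6.3.1.2) include all four factors. The immunogenicity ANCOVA (6.4.1) includes age category, GOLD grade and country besides the pre-dose concentration.

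**Baseline.** The EXACT-PRO baseline is each subject's mean of the daily scores recorded from Screening up to Visit 1. The rule for a sparse diary is: "If fewer than 4 days scores are available, the EXACT-PRO baseline score cannot be calculated, and it will result as missing". For the questionnaires generally, "missing items will not be imputed and subjects with partial data will be excluded". Nothing is said about a subject who has follow-up scores but no baseline.

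**Schedule.** Section 2 gives "Epoch 001: Screening Visit (Day -28 to Day -1") and says "The allowed maximum interval between Screening Visit and Visit 1 is 29 days". It states no minimum. EXACT-PRO is completed once a day: "Daily in the evening throughout the study (including during AECOPD").

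**The concern.** Minimisation forces the arms to be alike on the four factors, so chance differences in those factors hardly contribute to the treatment difference. An ANCOVA without them leaves their variance in the residual and computes a standard error as if allocation had been simple. If the factors predict the score beyond baseline, that standard error is too large and the test runs below its nominal level.

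Section 6.6.2 attaches a significance threshold of p<0.1 to these comparisons, and section 8 places health-related quality of life in the Priority 1 analyses for the main study report. An unnecessarily conservative test could miss a signal there. The plan gives no reason for departing from its own practice in the primary model.

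The baseline rule is a separate, smaller matter. An ANCOVA with a missing covariate and no imputation omits the subject, so someone with about 15 months of diary data can be absent from every EXACT-PRO comparison.

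**Working it through.** The SAP states no power or precision figure for EXACT-PRO, so there is none to reproduce.

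**1. Omitted factors**

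Inputs from the SAP: about 600 subjects, 1:1; D = 90%; four factors with 8, 3, 2 and 2 levels, hence 7 + 2 + 1 + 1 = 11 degrees of freedom; two-sided threshold 0.10. When the arm totals differ, the balancing arm is chosen with probability 0.9 + 0.1 × 0.5 = 0.95.

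Assumed, because the SAP gives no value: the partial R² of the four factors given baseline.

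Excess interval width is 1/√(1 − R²) − 1. If minimisation removes essentially all of the factors' contribution to the estimate, the actual type I error is the two-sided normal tail beyond 1.645/√(1 − R²).

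| Partial R² (assumed) | Width ratio | Effective critical value | Actual level at nominal 0.10 |
|---|---|---|---|
| 0 | 1.000 | 1.645 | 0.100 |
| 0.03 | 1.015 | 1.670 | 0.095 |
| 0.05 | 1.026 | 1.688 | 0.091 |
| 0.10 | 1.054 | 1.734 | 0.083 |
| 0.20 | 1.118 | 1.839 | 0.066 |

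A simulation of the section 11.3 algorithm checks this (600 subjects, 4,000 replicates; factor distributions and a baseline correlation of 0.7 assumed):

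| Partial R² | Model SE without / with factors | Ratio | True spread without / with | Type I without / with |
|---|---|---|---|---|
| 0 | 0.0583 / 0.0583 | 1.000 | 0.0591 / 0.0591 | 0.102 / 0.103 |
| 0.05 | 0.0584 / 0.0569 | 1.026 | 0.0573 / 0.0574 | 0.090 / 0.100 |
| 0.10 | 0.0584 / 0.0554 | 1.054 | 0.0538 / 0.0538 | 0.082 / 0.096 |
| 0.20 | 0.0583 / 0.0521 | 1.119 | 0.0532 / 0.0531 | 0.069 / 0.104 |

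The Monte Carlo standard error of a rate near 0.10 is √(0.1 × 0.9 / 4000) ≈ 0.005, so formula and simulation agree. The true spread of the estimate is the same with and without the factors; only the reported standard error changes. Spending 11 degrees of freedom out of about 600 costs nothing visible when R² = 0.

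**2. Missing baseline**

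Evenings available if the screening evening counts: Day −4 gives 4, Day −3 gives 3, Day −2 gives 2, Day −1 gives 1. If it does not count, Day −4 gives 3. On the SAP's outer window, screening on Day −3 or later cannot yield 4 scores. Missed entries have the same effect at any interval.

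The share affected is not in the SAP. With a share d dropped, the standard error rises by 1/√(1 − d) − 1. Power is for an assumed 0.2 SD effect at two-sided 0.10.

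| d (assumed) | Left of 600 | SE increase | Power |
|---|---|---|---|
| 0 | 600 | 0% | 78.9% |
| 5% | 570 | 2.6% | 77.1% |
| 10% | 540 | 5.4% | 75.1% |
| 20% | 480 | 11.8% | 70.7% |

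**The case against.** The strongest reply is that the planned model is valid. A prespecified ANCOVA on baseline is a sound analysis, EXACT-PRO is tertiary, and section 6.6.2 itself calls these comparisons exploratory, unadjusted for multiplicity and to be read with caution. No section promises that the quality-of-life models will carry the minimisation factors, so nothing is contradicted. The error, if there is one, is on the cautious side. All of this stands and sets the priority of the point, but it does not argue against a change that costs almost nothing.

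Several stronger readings are tempting and not supported:

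- **That the estimate is biased or noisier.** It is neither. Minimisation already balances the factors, and the simulated spread is the same under both models.
- **That the intervals are necessarily too wide.** This depends on a partial R² that the SAP does not give. At zero there is no effect.
- **That the argument applies equally to every period.** The Exacerbation period contains only subjects who had an event. That subset is formed after randomisation, and minimisation does not guarantee balance within it.
- **That the schedule alone will cause missing baselines.** Day −28 to Day −1 is an outer window, and section 2 refers to the protocol for details. The protocol may set a minimum interval.
- **That dropping these subjects biases the comparison.** Randomisation is at first dose, after the baseline diary, so this missingness precedes allocation. The subjects can still appear in the descriptive tables, and their omission from the ANCOVA is implied, not stated.

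The 4-day rule is also a sensible guard against an unreliable baseline. The gap is in what happens when it is not met.

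**Conclusion.** The point holds as an improvement, not as an error that threatens a conclusion. For the Treatment, Follow-up and 3-month sub-periods, omitting the factors used for allocation makes the intervals about 1.5% to 5% too wide for an assumed partial R² of 3% to 10%. At R² of 0.05 to 0.10 the test runs at about 0.08 to 0.09 against a nominal 0.10. Both effects vanish if the factors add nothing beyond baseline.

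The loss of subjects without a 4-day baseline is a secondary matter of power. Its size is unknown, and the percentages above are illustrations only.

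**What to change.** 1. Add country, GOLD grade, exacerbation history and age group to the EXACT-PRO ANCOVA for the Treatment, Follow-up and 3-month sub-periods. In the Exacerbation period the same terms may be used, but should be described as ordinary covariate adjustment in a post-randomisation subset.
2. First reconcile the age categories: section 11.3 minimises on 40–60 and 61–80, while the analysis models use 40–59 and 60–80. A subject aged 60 falls in different groups under the two.
3. State how a missing baseline is handled. Keep the subject by setting the covariate to the pooled baseline mean, the same value in both arms, with a missing-baseline indicator. Report the complete-baseline analysis as a sensitivity analysis.

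The cost is SAP wording and a few model terms, with no new data.

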3.3. Tertiary objectives

- To evaluate the effect of the investigational vaccine on the presence, acquisition/apparition and load of NTHi and/or Mcat at stable visits and AECOPD by PCR.
- To evaluate the effect of the investigational vaccine on the presence, acquisition/apparition and load of NTHi and/or Mcat at stable visits and AECOPD in a subset of sputum samples by culture.
- To explore the efficacy of the investigational vaccine as compared to placebo with respect to the rate of all AECOPDs and by severity (i.e. mild, moderate or severe) associated with NTHi and/or Mcat detected in a subset of sputum samples by culture.
- To explore the impact of the investigational vaccine on health-related quality of life (HRQOL).
- To explore the impact of the investigational vaccine on use of medication for COPD and Healthcare Resource Utilisation.
- To explore the impact of the investigational vaccine on lung function.
- To describe selected biomarkers in stable COPD and during AECOPD.
- To explore the T helper profile of the PD-, PE-, PilA-, UspA2-specific CD4⁺/ CD8⁺ T cell responses.

CONFIDENTIAL

207489 (NTHI MCAT-002)

Statistical Analysis Plan Amendment 2 FDA Final Draft

- To collect blood and sputum samples for assay development, for lung microbiome analysis, to explore the level of inflammation (into the lung) and/ or for additional evaluation of the immune responses to the investigational vaccine and to other potential pathogens involved in AECOPD.
- To explore the data for an immune correlate of protection.

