COPD Assessment test (CAT) is a patient-completed questionnaire assessing globally the impact of COPD (cough, sputum, dyspnoea, chest tightness) on health status. It constitutes of 8 items each scoring from 1 to 5. The Total score is given by the sum of the single item scores and it ranges from 0 to 40. Higher scores denote a more severe impact of COPD on patient's life.

CAT questionnaire will be provided to all enrolled patients at Screening, Day 271 and Day 451 (end of study), and at each AECOPD visit.

Descriptive statistics

Descriptive statistics (N, mean, SD, median, Q1 and Q3, min and max) on the CAT total score (obtained as sum of the scores of 8 single items) will be reported by scheduled visits (stable visits), by AECOPD visit and by each treatment group.

Data will be also represented via line-chart for the total score at each time points (screening, Day 271, Day 415 and any AECOPD visit) together with the 95% confidence interval around the mean of the total score.

Within group change and CAT responders

For each group and at each time point (Screening, Day 271 and Day 421), the mean of total score together with SD will be reported and a pair t-test will be performed to compare screening scores with scores at Day 271 and at Day 421.

CONFIDENTIAL

207489 (NTHI MCAT-002)

Statistical Analysis Plan Amendment 2 FDA Final Draft

Moreover, the percentage of “CAT responder” subjects will be calculated at Day 271 and 421. A “CAT responder” is defined as a subject with at least a 2 units improvement (Decrease in total score) with respect to the baseline (Screening)

Between groups comparison

Differences between groups will be analysed in terms of difference in mean for each time points (Day 271 and Day 421) by one-way ANOVA model on the total scores, with vaccine group as factor.

CAT Score at AECOPD Visit

N, mean, SD, median, Q1 and Q3, min and max CAT score during AECOPD visit will be displayed according to the number and severity of AECOPD event.

St. George's Respiratory Questionnaire assessment (SGRQ-C)

The St. George's Respiratory Questionnaire (SGRQ) is composed of 76 items that are weighted to produce three component scores: Symptoms: measuring distress caused by respiratory symptoms, Activity: measuring the effect of difficulties in mobility and physical activity, and Impact: quantifying the psychosocial impact of the disease.

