A “Total” score is also computed as sum from all component items score, thus providing a global estimation of the patients respiratory health. Each of these scores ranges from 0 to 100, a score of 100 indicating maximum disability [Jones, 1991]

SGRQ-C will be provided to all enrolled patients at Screening, Day 271 and Day 451 (end of study), and at each exacerbation visit.

Descriptive statistics

Descriptive statistics (N, mean, SD, median, Q1, Q3, min and max) on the SGRQ-C (total score and symptoms, activity and impacts component scores) will be reported by scheduled visits (stable visits), at each AECOPD visit and by each treatment group.

Mean score for each component (symptoms, activity and impacts) and mean total scores will be also represented via line-chart at each time points (screening, Day 271, Day 415 and any AECOPD visit) together with the 95% confidence interval around the mean.

Within group change and SGRQ-C responders.

For each group and at each time point (Screening, Day 271 and Day 421), the mean of each component score and the mean of total score together with SD will be reported and a pair t-test will be performed to compare screening scores with scores at Day 271 and at Day 421. Moreover, the percentage of “SGRQ-C responder” subjects will be calculated at Day 271 and 421. A “SGRQ-C responder” is defined as a subject with an improvement of more than 4 unit (Decrease in total score) with respect to the baseline (Screening).

CONFIDENTIAL207489 (NTHI MCAT-002)
Statistical Analysis Plan Amendment 2 FDA Final Draft**Between groups comparison**

For all components and for the total scores, differences between groups will be analysed in terms of difference in mean for each time points (Day 271 and Day 421) by one-way ANOVA model on the total scores, with vaccine group as factor.

SGRQ-C at AECOPD Visit

N, mean, SD, median, min and max, of each component scores and of total score during AECOPD visit will be displayed according to the number and severity of AECOPD event.

Use of medication to treat (AE)COPD and Healthcare utilization (HCU)

Frequency table on the number and type of healthcare utilisation (Physician's office, Visit to Urgent Care, Visit to Emergency Department, Hospitalization) during entire study period will be presented overall and by vaccine group.

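### CAT and SGRQ-C: within-arm p-values fall under the p<0.1 rule, responders get no between-arm contrast, and the between-arm ANOVA omits the Screening score

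*SAP*

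**What the plan says.** Section 3.3 of the SAP (Amendment 2) lists, as a tertiary objective, exploring the impact of the vaccine on health-related quality of life. Section 6.6.2 sets the common rule for these analyses: they are exploratory, and "a p-value <0.1 will be considered statistically significant, however 2-sided 95% CIs will be computed to show precision of estimation". It adds that "All comparisons should be interpreted with caution considering that there will be no adjustment for multiplicity".

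For each of CAT and SGRQ-C the section then plans three things.

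- **Within-arm change.** For CAT, in each group, "a pair t-test will be performed to compare screening scores with scores at Day 271 and at Day 421". For SGRQ-C, "the mean of each component score and the mean of total score together with SD will be reported and a pair t-test will be performed" in the same way, so three components and the total are each tested.
- **Responders.** The percentages of CAT and SGRQ-C responder "subjects will be calculated at Day 271 and 421". A CAT responder has a decrease of at least 2 units from Screening, and an SGRQ-C responder a decrease of more than 4. The between-groups paragraphs that follow do not mention responders.
- **Between-arm comparison.** Mean scores at each follow-up are compared "by one-way ANOVA model on the total scores, with vaccine group as factor"; for SGRQ-C this covers the components and the total.

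For EXACT-PRO, the same section compares the arms by ANCOVA with the screening score as covariate. Section 7 ties the p<0.1 reference for tertiary objectives to comparative analysis. Section 8 places the quality-of-life objective in Priority 1, Step 2, which is reported in the full clinical study report.

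**The concern.** The objective asks whether the vaccine changes quality of life, so the relevant null is no difference between vaccine and placebo. The paired t-tests have another null: that mean change from Screening is zero in one arm. Seasonal change, regression to the mean, disease progression or better care during the trial would move both arms and make that test reject, with no vaccine effect. Under the section's rule such a result is still called statistically significant.

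The responder percentages raise a related problem. Random variation makes many subjects responders, so one arm's percentage is not interpretable alone, and no contrast of the two arms is named. Elsewhere among the tertiary analyses (sections 6.6.1.2 and 6.6.1.3), acquisition and apparition percentages are paired with a between-group risk ratio.

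The ANOVA does address the vaccine question for mean scores. It ignores the Screening score, however, and so gives up precision and leaves chance baseline imbalance uncorrected.

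At stake is the reading of this part of the study report: improvement in the vaccine arm, or significance in one arm and not in the other, could be taken for benefit.

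**Working it through.** The SAP gives no sample size, expected change, SD or error rate for CAT or SGRQ-C, so there is no planned figure to reproduce. From the SAP: p<0.1, unadjusted; about 300 subjects per arm; two follow-up visits; the responder thresholds. Assumed: 250 evaluable per arm (range 200-300), SD of change 5-8 for CAT and 10-14 for SGRQ-C, an inert vaccine, and the same drift in both arms.

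**1. Number of within-arm tests.** CAT: 1 score × 2 arms × 2 visits = 4. SGRQ-C: 4 scores × 2 × 2 = 16. In total 20, of which 10 are in the vaccine arm.

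**2. Rejection by one paired t-test.** With d = mean change / SD of change, the statistic is noncentral t with n − 1 degrees of freedom and noncentrality d√n, tested two-sided at 0.10. For n = 250 and d = 0.10, the noncentrality is 0.10 × √250 = 1.58, and the test rejects 47% of the time.

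| n per arm | d = 0 | 0.05 | 0.10 | 0.15 | 0.20 | 0.30 |
|---|---|---|---|---|---|---|
| 200 | 10% | 18% | 41% | 68% | 88% | 99.5% |
| 250 | 10% | 20% | 47% | 76% | 93% | 99.9% |
| 300 | 10% | 22% | 53% | 83% | 97% | 100% |

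For CAT, d = 0.10 is a drift of 0.10 × 5 = 0.5 unit at SD 5 and 0.10 × 8 = 0.8 unit at SD 8.

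**3. Significant in the vaccine arm only, arms truly equal.** With rejection probability p in each independent arm, this is p(1 − p), here for one score at one visit with n = 250:
- d = 0: 0.10 × 0.90 = 9%
- d = 0.10: 0.474 × 0.526 = 25%
- d = 0.20: 0.934 × 0.066 = 6%

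**4. At least one significant within-arm test, no change at all.** If the tests were independent: 1 − 0.9^10 = 65% for the vaccine arm and 1 − 0.9^20 = 88% for both arms. In simulation (250 per arm, 3000 runs, assumed correlations of changes 0.3-0.6 between scores and 0.5-0.6 between visits): 47-59% and 72-83%.

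**5. Responder share with zero mean change, normal changes.**
- CAT, integer scores, so a cut at −1.5: Φ(−1.5/5) = 38% to Φ(−1.5/8) = 43%. With a cut at −2 and no continuity correction: 35-40%.
- SGRQ-C: Φ(−4/10) = 34% to Φ(−4/14) = 39%.

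**6. Between-arm comparison.** In the same simulations, comparing CAT change between arms at the last visit at p<0.1 rejected 9.5-10.9% of the time for d = 0, 0.1 and 0.2. Shared drift cancels.

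**7. Cost of leaving out the Screening score.** With correlation r between Screening and follow-up, ANCOVA has about (1 − r²) of the ANOVA residual variance: 0.75 at r = 0.5 and 0.51 at r = 0.7. The SAP gives no r.

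**The case against.** The strongest defence is that the SAP does test the vaccine effect. The ANOVA follows directly after the paired tests, and those sit under a within-group heading. Nowhere does the SAP say that they answer the vaccine question. If both arms drift, rejecting zero change is correct for the null tested, and harm needs a misreading. This stands in part: a reader might infer that section 6.6.2 has no test of vaccine effect on CAT or SGRQ-C, and that would be wrong. But the section's significance rule does not separate the two kinds of test, and its caution concerns multiplicity, not which null is tested.

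Section 7 already links p<0.1 to comparative analysis. That is true, so the two sections need aligning, and section 7 supports the change proposed here.

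On responders, section 6.6.2 promises 95% CIs in general, and section 11.1 gives interval methods for a proportion and for a difference in proportions. A claim that precision is missing altogether would therefore go too far, and both percentages can be seen side by side. What remains is that no responder contrast is scheduled.

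Finally, the objective is tertiary, exploratory and flagged for caution. This limits the weight of the point, but correcting it costs very little.

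**Conclusion.** The point holds within limits. The within-arm p-values count as significant under section 6.6.2 without bearing on vaccine effect, responders have no between-arm contrast, and the between-arm model omits a baseline score that the same section uses for EXACT-PRO.

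A reader might go further and infer that a significant result is likely even if the vaccine does nothing. For a single test the SAP does not support this: rejection is 10% without drift and passes 50% only if both arms move by roughly 0.10-0.15 SD, and the document gives neither drift nor SD. At least one significant result among the 20 unadjusted tests is likely even without drift, but that is multiplicity, which the section acknowledges. Nor can the responder percentages be significant, since they are not tests; their weakness is that about 34-43% would arise with zero mean change.

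All sizes rest on the assumed 250 evaluable subjects per arm, SDs, equal drift and, for the joint figures, correlations. No primary or secondary conclusion is affected.

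**What to change.** In section 6.6.2, for both CAT and SGRQ-C:

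1. Replace the paired t-tests by mean change from Screening in each arm with a 95% CI and no p-value.
2. Limit the p<0.1 reference to vaccine-versus-placebo comparisons, in line with section 7.
3. Add the vaccine-minus-placebo difference in responder percentage at each follow-up visit with a 95% CI. Name one method already in the SAP: the Miettinen-Nurminen interval of section 6.4.1 or the standardised asymptotic interval of section 11.1.
4. Replace the one-way ANOVA by an ANCOVA with vaccine group as factor and the Screening score as covariate, as for EXACT-PRO.

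While these paragraphs are open, reconcile the last time point: the questionnaires are scheduled at Day 451, the tests name Day 421 and the line charts Day 415.

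The cost is SAP wording and small changes to the questionnaire tables; no new data are needed. The only downside is that within-arm p-values are no longer shown.
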